Title: Personalized Lifestyle Intervention and Weight Control ID:

2018-12-006

NCT04079972

1. Background

In South Korea, the leading causes of death are cancer and cardiovascular diseases, and obesity is a major risk factor for these chronic conditions. As dietary habits in South Korea have become increasingly Westernized, the prevalence of obesity has risen rapidly. Therefore, discovering effective strategies for obesity prevention and weight loss is a crucial public health priority.

The principle of weight loss is simple—caloric intake must be lower than caloric expenditure—but achieving and maintaining weight loss is considerably more difficult in practice. Fewer than 20% of individuals who lose approximately 10% of their initial body weight maintain that loss for over a year, highlighting the need for sustainable and efficient approaches.

Dietary strategies for weight control are often categorized based on macronutrient composition (carbohydrates, proteins, fats), yet there remains no consensus on which approach is most effective. Evidence remains divided between those emphasizing low-carbohydrate diets and those suggesting that total caloric intake, rather than macronutrient ratio, is more important for weight loss and metabolic improvement.

Additionally, East Asians tend to have less skeletal muscle mass than Westerners despite having a similar or lower BMI, which increases their risk of metabolic diseases. Therefore, developing interventions that effectively improve muscle mass and strength is also essential.

[figure not shown]
Another key factor for sustainable weight management is emotional regulation. Emotional regulation both influences and is influenced by dietary and exercise habits, making it an important component to consider in weight control research.

A major limitation of many previous studies is the lack of consideration for individual differences. Evidence suggests that macronutrient preference, metabolic capacity, muscle response to exercise, and emotional regulation vary by genetic profile. In the era of precision medicine, it is increasingly important to determine whether genetically tailored diet and lifestyle interventions—those accounting for individual genetic predispositions—can lead to more sustainable weight loss and improved health outcomes compared with non-tailored approaches. The results from this study could provide valuable insight into resolving inconsistencies in the current literature.

2. Objective

- This randomized controlled trial aims to determine whether awareness of personal genetic information related to obesity improves weight management outcomes among overweight and obese individuals.
- Eating habits are typically formed over a long period and are difficult to modify without a strong motivator (e.g., a medical diagnosis). However, given the symbolic and personalized nature of genetic information, awareness of one's genetic profile may serve as a powerful trigger for behavioral change. Therefore, individuals who receive their genetic results accompanied by genotype-tailored recommendations are expected to demonstrate greater improvements in weight and related indicators compared with those who do not. Specifically, the study seeks to identify characteristics of individuals who voluntarily modify their diet or lifestyle after learning about their genetic information and tailored lifestyle recommendations, and to examine subsequent changes in obesity and health indicators. If participants' habits shift toward a genetically tailored lifestyle, such personalized approaches are expected to reduce physiological stress, enhance adherence, and yield sustainable improvements in weight and metabolic outcomes.

3. Design

● Randomized Controlled Trial:

- **Subjects:** 53 overweight or obese young adults.
- **Randomization:** Participants were randomly assigned to two groups (experimental and control) using a computer-generated randomization sequence.
- **Experimental group (27 participants):** Participants received their obesity-related genetic test results (including *FTO*, *MC4R*, and *BDNF*) along with genotype-tailored lifestyle recommendations encouraging healthy behaviors such as reducing fat intake, limiting snacking, and avoiding emotional eating.
- **Control group (26 participants):** Participants received genetic test results limited to non-obesity-related traits (e.g., beauty-related genes). No lifestyle recommendations were provided. Obesity-related genetic results were disclosed only after completion of the final follow-up.
- **Follow-up:** Questionnaire surveys and body composition measurements were conducted at baseline, approximately 5 months after randomization, and at study completion (up to 17 months).

- **Inclusion Criteria:**

1. Korean adults aged 18 and older who are interested in weight management through dietary/exercise therapy.
2. Individuals who can participate consistently in the study for 2 years.

- **Exclusion Criteria:**

1. Individuals currently suffering from illnesses requiring regular treatment in a hospital.
2. Individuals currently taking long-term prescribed medications.
3. Individuals diagnosed with an eating disorder or mental illness (e.g., depression, panic disorder) by a physician.
4. Individuals who have undergone gastric surgery for weight loss.
5. Individuals who have undergone heart surgery or cancer surgery.
6. Individuals suffering from severe anemia.
7. Individuals who are unable to exercise.
8. Pregnant or breastfeeding women, and women planning to become pregnant within 2 years.

4. Outcome assessment Method

- **Single Gene Variant Testing**

- We will evaluate single-nucleotide polymorphisms (SNPs) that may influence weight control. Key examples include genes related to energy metabolism (FTO), muscle strength (INSIG2), mood (BDNF), and taste perception (TAS2R38). Knowledge of such variants may help identify dietary and behavioral strategies that are more compatible with individual metabolic characteristics. For example, for the well-known obesity gene FTO, if a single gene variant such as rs9939609 is present, excess calories may be stored more readily as fat, making a low-calorie or low-fat diet more effective for weight control.

- **Obesity and Body Composition Measurements**

- We will assess various obesity-related parameters as follows:
 - ✓ **Body Weight Change:** The primary outcome, assessed at baseline, approximately 5 months after randomization, and at study completion (up to 17 months).
 - ✓ **Body Composition Change:** Body fat mass, body fat percentage, and skeletal muscle mass were assessed using a bioelectrical impedance analyzer (InBody720, Seoul, Korea). These secondary outcomes were measured at baseline, approximately 5 months after randomization, and at study completion (up to 17 months).

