Title: Personalized Lifestyle Intervention and Weight Control ID:

2018-12-006

NCT04079972

Proposal and Statistical analysis

In this study, we aim to conduct the most efficient analysis possible with limited research funding through appropriate epidemiological research designs and statistical analysis techniques.

1. Randomized Controlled Trial:

- **Subjects:** 53 overweight or obese young adults.
- **Randomization:** Participants were randomly assigned to two groups (experimental and control) using a computer-generated randomization sequence.
- **Experimental group (27 participants):** Participants received their obesity-related genetic test results (including *FTO*, *MC4R*, and *BDNF*) along with genotype-tailored lifestyle recommendations encouraging healthy behaviors such as reducing fat intake, limiting snacking, and avoiding emotional eating.
- **Control group (26 participants):** Participants received genetic test results limited to non-obesity-related traits (e.g., beauty-related genes). No lifestyle recommendations were provided. Obesity-related genetic results were disclosed only after completion of the final follow-up.
- **Follow-up:** Questionnaire surveys and body composition measurements were conducted at baseline, approximately 5 months after randomization, and at study completion (up to 17 months).
- **First Statistical Analysis (Intention to Treat Analysis):**
 - **Causal variable:** Knowledge of obesity-related genetic test results.
 - **Outcome variable:** Changes in body weight and body composition (body fat mass, body fat percentage, and skeletal muscle mass) compared to baseline.
 - **Statistical analysis to observe the correlation between causal and outcome variables:** The association between the causal and outcome variables will be examined using general linear regression and linear mixed models adjusted for baseline body mass index (BMI), physical activity, smoking status, and alcohol consumption.

- **Second Statistical Analysis (As Treated Analysis):**

- Although all participants in the experimental group received obesity-related genetic results and tailored lifestyle recommendations, adherence levels may vary. We will compare characteristics of those who reported behavioral changes after reading their genetic test results (“behavior changers”) with those who did not (“behavior maintainers”).

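### Do inclusion criteria without a BMI threshold or an upper age limit undermine a trial described as one of overweight or obese young adults?

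*Protocol*

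**What the plan says.** The Protocol's Objective (section 2) asks whether knowing one's obesity-related genetic information "improves weight management outcomes among overweight and obese individuals". The Subjects line in section 3 (Design) reads "53 overweight or obese young adults", and the SAP repeats it under its heading 1.

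The same Design section has two numbered inclusion criteria:

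- "Korean adults aged 18 and older who are interested in weight management through dietary/exercise therapy"
- "Individuals who can participate consistently in the study for 2 years"

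Eight exclusion criteria follow. The one closest to body weight is "Individuals who have undergone gastric surgery for weight loss". The one most likely to keep older people out is "Individuals currently taking long-term prescribed medications". Neither sets a BMI range or an age limit. In the SAP, BMI appears only as a covariate: the models are "adjusted for baseline body mass index (BMI), physical activity, smoking status, and alcohol consumption". Neither document gives a cut-off for overweight, obese or young.

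**The concern.** Eligibility criteria normally carry the definition of the trial population, and here they do not. A healthy 60-year-old of normal weight who wants to avoid gaining weight meets both inclusion criteria and need not trigger any exclusion, yet is not the kind of participant the Subjects line describes.

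The possible stakes are easy to see. Body weight change is the primary outcome. People with little weight to lose might respond less, which would shrink the average difference between arms and reduce power in a trial of only 53. Adjusting for baseline BMI as a main effect would not restore a treatment effect diluted in this way. The conclusion would also be stated for overweight and obese people, although the entry rule had not selected them. Finally, weight-loss advice given to people who are not overweight could raise a question of participant welfare.

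**Working it through.** **1. The texts side by side.**

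| Place | Weight status | Upper age |
|---|---|---|
| Protocol 2, Objective | overweight and obese | none |
| Protocol 3, Subjects line | overweight or obese | young adults |
| Protocol 3, two inclusion criteria | none | none (age 18 or more) |
| Protocol 3, eight exclusion criteria | none | none |
| SAP 1, Subjects line | overweight or obese | young adults |

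The gap in the numbered list is real. Both lists are numbered without a break (1–2 and 1–8), so it is not a product of text extraction.

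**2. Are the two descriptions incompatible?** No. An overweight young adult can satisfy the Subjects line and every criterion together. The Subjects line stands in the same Design section, above the criteria. Read as a whole, the section gives the population first and then adds further conditions. The list admits normal-weight people only if the Subjects line is set aside.

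**3. What do the documents say about who entered?** The Design text reports allocation, disclosure of results and follow-up in the past tense and gives achieved arm sizes. The Protocol has "Experimental group (27 participants" and a control group of 26; 27 + 26 = 53, which matches the Subjects line. That line therefore reads as an account of the people enrolled, and it implies that 0% were of normal weight.

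**4. What would dilution cost if it occurred?** The plan gives no effect size, SD, power or sample-size calculation, so there is no figure of its own to reproduce. As an illustration, take a two-sided 5% t-test with 27 and 26 participants (51 degrees of freedom, critical value 2.008). Let d be the standardised effect in overweight participants and f the share of entrants with no effect, with the SD held constant. The noncentrality parameter is

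d × (1 − f) × √(27 × 26 / 53) = d × (1 − f) × 3.639.

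The value d = 0.785 is chosen so that power starts at 80%:

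| f | d × (1 − f) | Noncentrality | Power |
|---|---|---|---|
| 0 | 0.785 | 2.857 | 80% |
| 0.1 | 0.7065 | 2.571 | 71% |
| 0.2 | 0.628 | 2.286 | 61% |
| 0.3 | 0.5495 | 2.000 | 50% |

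With d = 0.5 the same formula starts at 43%. The level depends entirely on the effect assumed, and the loss depends on an f that the documents put at zero. The first row of the table is the only one that agrees with the stated composition of the sample.

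**5. Age.** The Objective sets no upper age, so the target of inference is not limited to the young. The exclusions for regular hospital treatment, long-term medication, heart or cancer surgery and inability to exercise would remove many older adults in practice, although they are not an age limit. Nothing in the plan suggests that the effect would be distorted by age.

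**6. Welfare.** The advice described concerns fat intake, snacking and emotional eating; no calorie prescription or weight-loss target is stated. Diagnosed eating disorders, severe anaemia, pregnancy and breastfeeding are excluded.

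**The case for a change.** The strongest case for a change is that the Subjects line cannot serve as a reproducible entry rule. Its terms have no cut-offs, and the Background itself notes that East Asians can carry metabolic risk at a BMI similar to or lower than that of Westerners, so the choice of cut-off is not trivial. Because the line is written in the past tense, a reader cannot tell whether a BMI screen was applied, which one it was, or whether the sample simply turned out that way. Stating the limits used would take one line and no new data.

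Most of this stands as a comment on reporting: the operational definition is incomplete, and someone repeating the trial would need it. It does not show a fault in the design or the analysis. The main remedy would write down a rule already applied, which leaves the 53 participants, the models and the estimate as they are. The alternative remedy, rewording the population to match the criteria and showing the weight result by BMI category, is needed only if no weight restriction operated, and the stated composition of the sample points against that. Baseline BMI is in any case a planned covariate, so the composition of the sample can be described without any amendment.

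**Conclusion.** No change to the plan is called for. The numbered criteria leave out a BMI threshold and an upper age limit, but the Objective and both Subjects lines state the intended weight range, and the Subjects lines read as describing the people enrolled. On that reading the dilution is zero. The calculated fall in power from 80% to 71%, 61% or 50% rests on an assumed starting power, an assumed 10% to 30% share of non-overweight entrants and an assumed absence of effect in them. The documents support none of the three.

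This conclusion assumes that the Subjects line is accurate. The documents do not prove that a BMI screen was applied, but they contain no sign that anyone outside the described population was enrolled. What is left is a minor gap in definition, which a report of the baseline BMI and age distributions would ordinarily fill.

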Title: Personalized Lifestyle Intervention and Weight Control ID:

2018-12-006

NCT04079972

Proposal and Statistical analysis

In this study, we aim to conduct the most efficient analysis possible with limited research funding through appropriate epidemiological research designs and statistical analysis techniques.

1. Randomized Controlled Trial:

- **Subjects:** 53 overweight or obese young adults.
- **Randomization:** Participants were randomly assigned to two groups (experimental and control) using a computer-generated randomization sequence.
- **Experimental group (27 participants):** Participants received their obesity-related genetic test results (including *FTO*, *MC4R*, and *BDNF*) along with genotype-tailored lifestyle recommendations encouraging healthy behaviors such as reducing fat intake, limiting snacking, and avoiding emotional eating.
- **Control group (26 participants):** Participants received genetic test results limited to non-obesity-related traits (e.g., beauty-related genes). No lifestyle recommendations were provided. Obesity-related genetic results were disclosed only after completion of the final follow-up.
- **Follow-up:** Questionnaire surveys and body composition measurements were conducted at baseline, approximately 5 months after randomization, and at study completion (up to 17 months).
- **First Statistical Analysis (Intention to Treat Analysis):**
 - **Causal variable:** Knowledge of obesity-related genetic test results.
 - **Outcome variable:** Changes in body weight and body composition (body fat mass, body fat percentage, and skeletal muscle mass) compared to baseline.
 - **Statistical analysis to observe the correlation between causal and outcome variables:** The association between the causal and outcome variables will be examined using general linear regression and linear mixed models adjusted for baseline body mass index (BMI), physical activity, smoking status, and alcohol consumption.

- **Second Statistical Analysis (As Treated Analysis):**

- Although all participants in the experimental group received obesity-related genetic results and tailored lifestyle recommendations, adherence levels may vary. We will compare characteristics of those who reported behavioral changes after reading their genetic test results (“behavior changers”) with those who did not (“behavior maintainers”).
- **Causal variable:** Causal variable: Degree of self-reported dietary and lifestyle change according to genotype from baseline to approximately 5 months after randomization.
- **Outcome variable:** Changes in body weight and body composition compared to baseline.
- **Statistical analysis:** Linear regression or mixed models will be used to evaluate associations between variables.
- **(Additional Analysis):** Within the experimental group, baseline characteristics of behavior changers and maintainers will be compared using chi-square tests or t-tests.

- **Ethical Issues:** For the control group, only non-obesity-related genetic information was provided during the study period, and obesity-related genetic results were disclosed after the study ended. Therefore, no ethical issues were anticipated.

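### The intention-to-treat analysis names genetic knowledge as the cause, but the randomised arms differ in knowledge and tailored advice together

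*SAP*

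**What the plan says.** SAP section 1, under the First Statistical Analysis (intention to treat), gives the causal variable as "Knowledge of obesity-related genetic test results". The outcomes are changes from baseline in body weight and body composition. The models adjust for baseline BMI, physical activity, smoking and alcohol.

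The first bullet of Protocol section 2 (Objective) is framed in the same way: the trial "aims to determine whether awareness of personal genetic information related to obesity improves weight management outcomes among overweight and obese individuals". The second bullet states a broader hypothesis: "individuals who receive their genetic results accompanied by genotype-tailored recommendations are expected to demonstrate greater improvements in weight and related indicators".

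The arm descriptions are the same in Protocol section 3 and SAP section 1. The experimental arm received obesity-gene results "along with genotype-tailored lifestyle recommendations encouraging healthy behaviors such as reducing fat intake, limiting snacking, and avoiding emotional eating". The control arm received results for unrelated traits only, and "No lifestyle recommendations were provided". The SAP's Ethical Issues paragraph confirms that for controls "only non-obesity-related genetic information was provided during the study period". The Second Statistical Analysis opens by noting that "all participants in the experimental group received obesity-related genetic results and tailored lifestyle recommendations".

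**The concern.** A variable that the SAP calls causal should describe what randomisation changed. Here the label names one part of the experimental intervention and leaves out the other. The omitted part is direct behavioural advice, which could change weight whether or not a genotype is disclosed.

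The label belongs to the first analysis, and body weight is the primary outcome. If the arms differ, a report that follows the SAP's wording would say that knowing one's obesity genotype produced the difference. That is the question the Protocol's Objective puts first, and the design cannot answer it in that form.

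**Working it through.** The documents give no figure to reproduce on this point. The check is whether a knowledge-only effect can be identified from the arms as described.

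**Inputs**
- Experimental arm, 27 participants: obesity-gene results yes, recommendations yes (SAP section 1, Experimental group; the Second Statistical Analysis says this held for all of them).
- Control arm, 26 participants: obesity-gene results no, recommendations no, until after the final follow-up (SAP section 1, Control group and Ethical Issues).
- Total: 27 + 26 = 53, which agrees with the stated number of subjects.

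**Cross-classification during follow-up**

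| | Recommendations | No recommendations |
|---|---|---|
| Obesity-gene results | 27 | 0 |
| No obesity-gene results | 0 | 26 |

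Participants with one component but not the other: 0 of 53.

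**Identifiability**

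Let K = 1 if a participant had obesity-gene results and R = 1 if a participant had recommendations. In every participant K = R, so their correlation is 1. A design matrix with an intercept, K and R has 3 columns but rank 2.

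Write the mean change as a + b·K + c·R + d·K·R. Then:

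- experimental mean = a + b + c + d
- control mean = a
- difference between arms = b + c + d

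The trial estimates the sum b + c + d. It gives no information on b (knowledge), c (advice) or d (their interaction) separately. Any split of the sum fits the data equally well, including b = 0.

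**Can the planned models help?**
- The four covariates do not break the identity K = R, so adjustment leaves the rank deficiency in place.
- The mixed model uses repeated visits (about 5 months and up to 17 months), but K and R stay equal at every visit because controls learn their obesity-gene results only after the last one.

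**A possible further difference**

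Controls received non-obesity results. The documents do not say whether the experimental arm received them too. If it did not, the single contrast covers three differences instead of two. This is an open question, and the conclusion does not depend on it.

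**The case against.** The strongest reply is that the label is shorthand. Both arms are set out in full just above it, the sentence that opens the next analysis repeats that both components were given, and the second bullet of the Objective states the hypothesis for the package. An intention-to-treat analysis compares participants as assigned, and knowledge coincides with assignment here, so the calculation is the same under either label. Neither document yet draws the knowledge-only conclusion.

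Much of this stands. A careful reader can see what was compared, the package estimate is sound, and the harm arises only when the result is interpreted. The zero count of discordant participants would also hold in any two-arm trial of a bundled intervention. It shows that the effects cannot be separated, and it does not measure how much would be misattributed.

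The reply does not remove the point. The arm descriptions say what was delivered, while the causal-variable line says what the effect will be attributed to, and the two disagree. The documents themselves list results and recommendations as separate items, so advice cannot be read as merely part of knowing the result. The second bullet of the Objective shows that the documents hold two versions of the exposure, and the SAP took the narrower one for its first analysis.

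**Conclusion.** The concern holds. The intention-to-treat comparison estimates the effect of obesity-gene results plus tailored recommendations against unrelated results without recommendations. It cannot attribute a difference to genetic knowledge. One randomised contrast covers two certain differences, and possibly a third. The share due to knowledge is not identified at all, so no size can be put on the possible misattribution.

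This rests on the arms having been delivered as the documents describe. It does not call into question the validity of the package comparison. The point should be fixed because the label determines what the first analysis may claim.

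**What to change.** In SAP section 1, First Statistical Analysis, replace the causal-variable line with text such as:

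> *Randomised assignment to the package of obesity-gene results and advice tailored to genotype, versus results for unrelated traits with no lifestyle advice. This analysis estimates the effect of the package and does not support a claim about genetic knowledge alone.*

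In the same place, state whether the experimental arm also received the non-obesity results.

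Leave the first bullet of Protocol section 2 as written, and add a dated note that the design answers it only for the package. The documents describe the trial as already conducted, and rewriting the objective now would hide the question originally asked. The SAP change should be dated and explained for the same reason.

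The as-treated section also defines behaviour change by reference to the test results alone. That wording should change only if the questionnaire shows that participants were asked about the recommendations as well; the questionnaire is not in the documents.

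The cost is one replaced line with a limitation sentence, one clarification and one dated note. No arm, model, estimate, interval or p-value changes. What is given up is a claim about genetic awareness by itself, which the design could not support.

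### The ITT models omit sex, although both sexes appear eligible and no stratification by sex is described; pre-specifying it is a cheap improvement

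*SAP*

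**What the plan says.** SAP section 1, First Statistical Analysis, defines the outcomes as "Changes in body weight and body composition (body fat mass, body fat percentage, and skeletal muscle mass) compared to baseline". It fits linear regression and "linear mixed models adjusted for baseline body mass index (BMI), physical activity, smoking status, and alcohol consumption". Neither document adds sex to this list.

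The subjects are "53 overweight or obese young adults", 27 in the experimental arm and 26 in the control arm. Allocation is described only as coming from a computer-generated sequence. Stratification, blocking and minimisation are not mentioned, and the documents do not say that allocation was unstratified.

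Eligibility is in Protocol section 3. Inclusion criterion 1 admits "Korean adults aged 18 and older" and sets no restriction by sex. Exclusion criterion 8 removes "Pregnant or breastfeeding women, and women planning to become pregnant within 2 years", so women in general are eligible and men are not excluded. The sex mix of the enrolled participants is not given. Protocol section 4 makes body weight change the primary outcome and the body composition measures secondary.

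**The concern.** Three of the four ITT outcomes are fat mass, fat percentage and skeletal muscle mass. Sex is a plausible predictor of how much these change in absolute terms, and baseline BMI does not separate fat from muscle. With about 26 people per arm and no described feature that balances sex, the arms could differ noticeably in sex mix by chance.

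Two things are at stake. First, any variance in change that sex explains beyond the listed covariates stays in the residual and widens the interval. Second, if the baseline table shows a visible imbalance, the analysts must either report an estimate open to challenge or add sex after the fact, which looks data-driven. Pre-specification avoids that choice.

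**Working it through.** The documents give no SD, effect size, alpha, power or sex mix, so there is no planned figure to reproduce. The arm sizes (27 and 26) come from the SAP; every other input below is an assumption. The precision figures are for one follow-up with all 53 observed.

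**1. Chance imbalance.** Simple allocation of 53 people into 27 and 26, exact hypergeometric distribution:

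| Share of women (number of 53) | P(gap ≥ 10 points) | P(gap ≥ 20 points) |
|---|---|---|
| 50% (26) | 41% | 17% |
| 60% (32) | 41% | 17% |
| 70% (37) | 37% | 14% |
| 80% (42) | 50% | 4% |
| 90% (48) | 35% | 0% |

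The 10-point column is not monotone because the possible gaps are discrete.

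**2. Shift in the observed estimate.** Shift = gap × sex difference in change. The SE of the arm difference, in SD units, is sqrt(1/27 + 1/26) = 0.275.

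- Gap 0.20, sex difference 0.5 SD: 0.20 × 0.5 = 0.10 SD, and 0.10/0.275 = 0.36 SE.
- In kg for weight, with SD 5 kg and a sex difference of 2 kg: 0.20 × 2 = 0.4 kg. The SE is 5 × 0.275 = 1.37 kg, so the shift is 0.29 SE.

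For scale, the difference detectable with 80% power at two-sided 5% (assumed) is (1.960 + 0.842) × 0.275 = 0.77 SD.

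**3. Precision for weight.** The share of variance explained by sex is R² = p(1-p) × d²/SD², where p is the proportion of women and d the sex difference in change. The SE ratio is sqrt((1-R²) × 46/45). It assumes that the listed covariates use 5 df (53 - 2 - 5 = 46) and that sex uses one more. With SD 5 kg:

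| d (kg) | R², 50% women | SE ratio | R², 80% women | SE ratio |
|---|---|---|---|---|
| 1 | 0.010 | 1.006 | 0.0064 | 1.008 |
| 2 | 0.040 | 0.991 | 0.0256 | 0.998 |
| 3 | 0.090 | 0.964 | 0.0576 | 0.981 |

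If sex explains nothing, the ratio is sqrt(46/45) = 1.011, a cost of about 1%.

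**4. Precision for any outcome.** By the same formula, R² = 0.02, 0.05 and 0.10 give SE ratios of 1.001, 0.985 and 0.959. At an effect with 80% power without sex, power becomes 80.8%, 82.0% and 84.0% (normal approximation, without the df correction). For a body composition measure with a 0.5 SD sex difference and 50% women, R² = 0.25 × 0.25 = 0.0625 and the ratio is 0.979, about 2% off the SE.

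**The case against.** The strongest reply is that randomisation already deals with sex. The comparison is unbiased over repeated allocations, and its standard error allows for chance imbalance in any unmodelled covariate. That stands. A reader might infer that omitting sex biases the ITT comparison or invalidates its test; it does neither. What remains is precision and the estimate conditional on the allocation obtained.

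The outcomes are changes from baseline, so sex differences in level largely cancel. Only differences in change matter, and BMI, activity, smoking and alcohol may absorb some of these. The precision figures treat sex as unrelated to those covariates, so they overstate the gain for a given sex difference if there is overlap. Putting each outcome's own baseline in the model would also shrink the gain for fat and muscle mass.

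Further limits also stand:

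- A reader might take it as fact that the trial enrolled both sexes and that allocation was unstratified. Both are inferences, one from eligibility and one from silence. An even sex mix is also the assumption most favourable to the point.
- Larger gains can be produced for muscle mass. A 1 SD sex difference at 50% women gives R² = 0.25 and an SE ratio of 0.876, equivalent to about 30% more participants (1/0.876² = 1.30). Nothing in the documents supports a difference of that size.
- The case does not extend to age. The participants are described as young adults, and the documents give nothing from which to size an age effect.
- The SAP's opening, "we aim to conduct the most efficient analysis possible with limited research funding", states an aim tied to funding and design. It is not a promise of minimum variance that the covariate list breaks.

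**Conclusion.** The point holds as a cheap improvement, for precision and protection against chance imbalance. Sex is absent from the ITT covariates, both sexes appear eligible, and no described design feature balances it.

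The size is modest. For the primary outcome, adding sex changes the SE by about +0.6% to -3.6% (sex difference 1 to 3 kg, SD 5 kg, 50% women). At 80% women there is essentially no gain at 1 or 2 kg. For body composition the gain may be larger, but its size cannot be determined from the documents. A 20-point imbalance is a realistic possibility (14-17%) if women make up 50-70% of the sample, and unlikely at 80% or more. If only one sex was enrolled the point lapses, and near 90% women it largely does.

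**What to change.** First confirm the enrolled sex mix. If both sexes were enrolled, add to the First Statistical Analysis: *Every ITT model for weight, fat mass, fat percentage and skeletal muscle mass will also include sex as a fixed covariate (1 df), chosen for its expected prognostic value. The same models without sex will be shown as a sensitivity analysis.* The SAP describes the analysis in the future tense but recruitment and follow-up in the past tense. If arm-level data have already been seen, the addition should be labelled post hoc.

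The cost is a line or two of SAP wording and one degree of freedom, about 1% on the SE if sex proves uninformative. New measurements should not be needed: exclusion criterion 8 applies only to women, so sex should already be known from screening.
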